#### 7.4 Emergency unblinding

Before the crossover at 12 months, unblinding may be done only in cases of an emergency. Follow the directions below to unblind patient treatment. Please note that if a treatment assignment is unblinded, the patient must discontinue protocol therapy.

Emergency Unblinding Procedures:

Examples of emergencies include 1) a life-threatening unexpected adverse event that is at least possibly related to the investigational agent and for which unblinding would influence treatment decisions; or 2) medication error, such as accidental overdose. Expected adverse events are listed in the "Toxicities" section below.

Contact the Alliance Executive Officer on call by calling

The institution must provide the following information to the Alliance Executive Officer:

- Alliance study ID ("A211102")
- Alliance patient ID number (e.g., "999999")
- Patient initials (e.g., "L,FM")
- Institution name
- Name and telephone number of treating physician
- Name and contact information of person requesting the unblinding procedure
- Name and contact information of person to inform of treatment assignment
- Reason for emergency unblinding

Please remember that emergency unblinding request may be authorized only by an Alliance Executive Officer, and emergency unblinding applies only if unblinding would influence management of the medical situation.

After the Executive Officer deems unblinding is warranted, the treatment assignment will be provided to the contact person at the treating site.

#### 8.0 DOSAGE MODIFICATION BASED ON ADVERSE EVENTS

#### 8.1 Summary

The major toxic effects of metformin which limit dose are gastrointestinal (GI) (nausea, abdominal bloating, and diarrhea). Dose adjustments, for reasons of GI side effects, will be as in the tables below. (Please note that none of the recommended dose adjustments requires splitting of study medication pills. Pills are not to be split or crushed, prior to taking, for any reason.) Breaks of up to 4 weeks consecutively or 8 weeks overall are allowed to ascertain the cause of symptoms. Beyond this, treatment is at the discretion of the treating physician.

#### 8.2 Dose modifications

Strictly follow the modifications in this table, until individual treatment tolerance can be ascertained. Thereafter, these modifications should be regarded as guidelines to define mild-to-moderate, but not debilitating, side effects. If multiple adverse events are seen, administer dose based on greatest reduction required for any single adverse event observed. Reductions or increases apply to treatment given in the preceding cycle and are based on adverse events observed since the prior dose.

8.2.1 If the patient has grade 3 or 4 diarrhea, metformin/placebo should be discontinued.

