## 8.2.2 Dose modification tables

| $\rightarrow$ $\rightarrow$ Use the NCI Common Terminology Criteria for Adverse Events (CTCAE) version 4.0* unless |                          |           |   |  |  |  |  |  |  |
|--|--------------------------|-----------|---|--|--|--|--|--|--|
| otherwise specified $\leftarrow$ $\leftarrow$  |                          |           |   |  |  |  |  |  |  |
| CTCAE  |                          |           | ACTION  |  |  |  |  |  |  |
| System/Organ/Class   | ADVERSE EVENT            | AGENT     | ACTION  |  |  |  |  |  |  |
|  |                          |           |   |  |  |  |  |  |  |
| BASED ON INTERVAL ADVERSE EVENT  |                          |           |   |  |  |  |  |  |  |
| Gastrointestinal   | Grade I                  | Metformin | Patient should be encouraged to remain on     |  |  |  |  |  |  |
| disorders  | Abdominal distansion     |           | study treatment for one week                  |  |  |  |  |  |  |
|  | Reating                  |           | For subjects who were unwilling to remain     |  |  |  |  |  |  |
|  | Diarrhea                 |           | on full dose after one week without study     |  |  |  |  |  |  |
|  | Nausea                   |           | drug follow the ramp-up procedure If          |  |  |  |  |  |  |
|  | Vomiting                 |           | Grade 1 symptoms persist or recur during      |  |  |  |  |  |  |
|  | Gastrointestinal         |           | the ramp-up or at full dose and the patient   |  |  |  |  |  |  |
|  | disorders – Other,       |           | is unwilling to continue, follow              |  |  |  |  |  |  |
|  | specify                  |           | instructions for Grade 2 toxicity.            |  |  |  |  |  |  |
|  |                          |           |   |  |  |  |  |  |  |
| Gastrointestinal   | $\geq$ Grade 2 or higher | Metformin | Reduce to one tablet per day for one week.    |  |  |  |  |  |  |
| disorders  |                          |           | If symptoms resolve or are Grade 1 only,      |  |  |  |  |  |  |
|  | Abdominal distension     |           | after one week, resume full dose (2 tablets   |  |  |  |  |  |  |
|  | Bloating                 |           | per day).                                     |  |  |  |  |  |  |
|  | Diarrhea                 |           | If symptoms persist or recur at Grade 2 or    |  |  |  |  |  |  |
|  | Nausea                   |           | higher, delay study treatment for 4 weeks,    |  |  |  |  |  |  |

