|  | Vomiting                 |           | then resume study treatment as follows:       |  |  |  |  |  |  |
|  | disorders Other          |           | remp up schedule (one tablet per day for 4    |  |  |  |  |  |  |
|  | specify                  |           | weeks then one tablet twice a day if          |  |  |  |  |  |  |
|  | speeny                   |           | tolerated) If toxicity persists or recurs the |  |  |  |  |  |  |
|  |                          |           | study drug should be adjusted to the          |  |  |  |  |  |  |
|  |                          |           | maximum dose that is tolerated with Grade     |  |  |  |  |  |  |
|  |                          |           | 1 toxicity or lower. A second attempt to      |  |  |  |  |  |  |
|  |                          |           | increase to full dose should be made 3        |  |  |  |  |  |  |
|  |                          |           | months later and if the full dose is not      |  |  |  |  |  |  |
|  |                          |           | tolerated at that time, the maximum           |  |  |  |  |  |  |
|  |                          |           | tolerated dose should be used for the         |  |  |  |  |  |  |
|  |                          |           | remainder of the 2-year (metformin group)     |  |  |  |  |  |  |
|  |                          |           | or 1-year (Placebo crossover group)           |  |  |  |  |  |  |
|  |                          |           | intervention.                                 |  |  |  |  |  |  |

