#### **13.0** TREATMENT/FOLLOW-UP DECISION AT EVALUATION OF PATIENT

#### **13.1** Discontinuation due to side effects

Patients who discontinue study medication before the completion of metformin due to side effects should still be followed per the test schedule for data collection time points. If the patient refuses, then the patient should be removed from study. Off Treatment Form must be submitted per the schedule of forms.

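### Grade 3–4 diarrhea falls under two conflicting rules: 8.2.1 stops study drug, the 8.2.2 table reduces and rechallenges, and nothing says which governs

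*Combined protocol and SAP*

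**What the plan says.** Four places in the combined protocol and SAP bear on this.

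- **8.1 Summary** refers gastrointestinal adjustments to the tables: "Dose adjustments, for reasons of GI side effects, will be as in the tables below". It makes no exception.
- **8.2 Dose modifications** opens with "Strictly follow the modifications in this table, until individual treatment tolerance can be ascertained"; after that point the modifications become guidelines.
- **8.2.1** gives a stop rule for one event at two grades: "If the patient has grade 3 or 4 diarrhea, metformin/placebo should be discontinued".
- **8.2.2 Dose modification tables** has a second gastrointestinal row, headed "Grade 2 or higher", which lists diarrhea among its events. Its first action is "Reduce to one tablet per day for one week". If symptoms clear or fall to grade 1, the woman goes back to two tablets a day. If they persist or return at grade 2 or above, treatment is delayed for 4 weeks and then restarted on the ramp-up schedule. If full dose is still not tolerated, she takes the highest dose she can tolerate, and another try at full dose follows 3 months later.

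Section 13.1 adds that women who stop for side effects "should still be followed per the test schedule for data collection time points".

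**The concern.** Grade 3 or 4 diarrhea meets the condition of both 8.2.1 and the second table row. One ends study drug; the other keeps the woman on it and plans a return to full dose. A site that works from the table, as 8.1 and 8.2 tell it to, would continue dosing a woman whom 8.2.1 takes off drug.

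Diarrhea is one of the dose-limiting toxicities named in 8.1 and one of the common reactions listed in 15.1.7, so this is the toxicity for which sites will consult these rules. What is at stake is the safety of the woman concerned and the same handling of the same event at every site.

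**Working it through.** The plan states no figure on this point. The check is a comparison of the texts, followed by simple dose arithmetic.

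**Which rule applies to which event**

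| Event | 8.2.1 | Second row of 8.2.2 | Conflict |
|---|---|---|---|
| Grade 2 diarrhea | silent | reduce, then resume or delay and rechallenge | no |
| Grade 3–4 diarrhea | discontinue | reduce, then resume or delay and rechallenge | **yes** |
| Other listed gastrointestinal events, grade 2 or above | silent | reduce, then resume or delay and rechallenge | no |

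The overlap is confined to grade 3–4 diarrhea.

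**Does any text rank the two rules?**

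- 8.1 and the opening of 8.2 point to the table and make no exception.
- The greatest-reduction sentence in 8.2 is limited to several adverse events occurring together. It does not settle two rules for one event.
- The allowance in 8.1 for treatment breaks, with physician discretion beyond them, does not rank the rules.
- 13.1 describes follow-up after a woman has stopped, not when she should stop.
- The legible table text contains no cross-reference to 8.2.1.

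**Dose given to one affected woman**

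Input: one tablet is 850 mg (7.1.1).

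- Week after the event, table row: 7 days × 1 tablet = 7 tablets; 7 × 850 = 5,950 mg. Under 8.2.1: 0.
- If symptoms clear or fall to grade 1, table row: 2 × 850 = 1,700 mg/day. Under 8.2.1: 0.
- If symptoms persist, table row: a 4-week delay, then a 4-week ramp-up of 28 × 1 tablet = 28 tablets; 28 × 850 = 23,800 mg. Under 8.2.1: 0.

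**Timing**

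In the first 4 weeks the dose is already one tablet a day (7.1.1), and women who cross over from placebo have a second such period (7.1.2). For an event in that window, the row's first action is no reduction at all: she stays on the same dose for a week and then goes to two tablets if symptoms settle. Early treatment is also when 8.2 asks for strict use of the table.

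**The case against.** The best reply is that only one reading gives both rules something to do. If the table governed grade 3–4 diarrhea, 8.2.1 would never operate. If 8.2.1 governs, the row still covers grade 2 diarrhea and the other gastrointestinal events, which need the open-ended heading because they have no stop rule of their own. Ending treatment is arguably not a dose adjustment in the sense of 8.1. Section 8.2.1 sits under the same heading as the instruction to follow the table, and 8.2 also describes the modifications as concerned with mild to moderate effects. The meaning of stopping is fairly clear too, since temporary interruptions are called breaks or delays and 13.1 deals with women who stop for side effects.

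Much of this stands. The specific-over-general reading is sensible and probably what was intended, and a permanent stop is the likeliest meaning in 8.2.1. The milligram figures arise only where a site follows the row instead of 8.2.1, and they describe exposure, not harm.

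It does not remove the conflict. The reading is an inference that no sentence states. The mild-to-moderate wording applies only after individual tolerance has been established, whereas the row itself extends upward without limit. A safety stop should not depend on staff at several sites working out precedence for themselves. Part of the table cell is damaged in the copy reviewed, so a lost qualifier cannot be wholly excluded, but the grade heading, the diarrhea entry and the actions are legible.

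**Conclusion.** The concern holds. For grade 3–4 diarrhea the protocol gives two incompatible instructions and does not say which prevails. The difference for an affected woman is 7 tablets (5,950 mg) against none in the following week. After that the row brings either a return to 1,700 mg/day or, after the delay, a 28-tablet (23,800 mg) ramp-up.

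The number of women cannot be computed because the documents give no rate for this event; it is probably very small. Because women who stop for side effects remain in follow-up, the primary analysis, sample size and power do not change. The conclusion assumes that the legible table text is complete on this point. The correction should be made because it concerns a safety instruction and costs almost nothing.

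**What to change.** Let 8.2.1 govern. In the second row of the 8.2.2 table, either restrict the diarrhea entry to grade 2 or add an exception such as: *except grade 3–4 diarrhea: discontinue per 8.2.1*. As an optional clarification, state in 8.2.1 that the discontinuation is permanent and that follow-up continues under 13.1.

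The cost is one line in the table and one sentence in 8.2.1, with no change to design, sample size or analysis.

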## 8.2.2 Dose modification tables

| $\rightarrow$ $\rightarrow$ Use the NCI Common Terminology Criteria for Adverse Events (CTCAE) version 4.0* unless |                          |           |   |  |  |  |  |  |  |
|--|--------------------------|-----------|---|--|--|--|--|--|--|
| otherwise specified $\leftarrow$ $\leftarrow$  |                          |           |   |  |  |  |  |  |  |
| CTCAE  |                          |           | ACTION  |  |  |  |  |  |  |
| System/Organ/Class   | ADVERSE EVENT            | AGENT     | ACTION  |  |  |  |  |  |  |
|  |                          |           |   |  |  |  |  |  |  |
| BASED ON INTERVAL ADVERSE EVENT  |                          |           |   |  |  |  |  |  |  |
| Gastrointestinal   | Grade I                  | Metformin | Patient should be encouraged to remain on     |  |  |  |  |  |  |
| disorders  | Abdominal distansion     |           | study treatment for one week                  |  |  |  |  |  |  |
|  | Reating                  |           | For subjects who were unwilling to remain     |  |  |  |  |  |  |
|  | Diarrhea                 |           | on full dose after one week without study     |  |  |  |  |  |  |
|  | Nausea                   |           | drug follow the ramp-up procedure If          |  |  |  |  |  |  |
|  | Vomiting                 |           | Grade 1 symptoms persist or recur during      |  |  |  |  |  |  |
|  | Gastrointestinal         |           | the ramp-up or at full dose and the patient   |  |  |  |  |  |  |
|  | disorders – Other,       |           | is unwilling to continue, follow              |  |  |  |  |  |  |
|  | specify                  |           | instructions for Grade 2 toxicity.            |  |  |  |  |  |  |
|  |                          |           |   |  |  |  |  |  |  |
| Gastrointestinal   | $\geq$ Grade 2 or higher | Metformin | Reduce to one tablet per day for one week.    |  |  |  |  |  |  |
| disorders  |                          |           | If symptoms resolve or are Grade 1 only,      |  |  |  |  |  |  |
|  | Abdominal distension     |           | after one week, resume full dose (2 tablets   |  |  |  |  |  |  |
|  | Bloating                 |           | per day).                                     |  |  |  |  |  |  |
|  | Diarrhea                 |           | If symptoms persist or recur at Grade 2 or    |  |  |  |  |  |  |
|  | Nausea                   |           | higher, delay study treatment for 4 weeks,    |  |  |  |  |  |  |
|  | Vomiting                 |           | then resume study treatment as follows:       |  |  |  |  |  |  |
|  | disorders Other          |           | remp up schedule (one tablet per day for 4    |  |  |  |  |  |  |
|  | specify                  |           | weeks then one tablet twice a day if          |  |  |  |  |  |  |
|  | speeny                   |           | tolerated) If toxicity persists or recurs the |  |  |  |  |  |  |
|  |                          |           | study drug should be adjusted to the          |  |  |  |  |  |  |
|  |                          |           | maximum dose that is tolerated with Grade     |  |  |  |  |  |  |
|  |                          |           | 1 toxicity or lower. A second attempt to      |  |  |  |  |  |  |
|  |                          |           | increase to full dose should be made 3        |  |  |  |  |  |  |
|  |                          |           | months later and if the full dose is not      |  |  |  |  |  |  |
|  |                          |           | tolerated at that time, the maximum           |  |  |  |  |  |  |
|  |                          |           | tolerated dose should be used for the         |  |  |  |  |  |  |
|  |                          |           | remainder of the 2-year (metformin group)     |  |  |  |  |  |  |
|  |                          |           | or 1-year (Placebo crossover group)           |  |  |  |  |  |  |
|  |                          |           | intervention.                                 |  |  |  |  |  |  |

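### Minor dosing-rule error in Section 8.2.2: a woman who balks during a repeat ramp-up is sent to a Grade 2 rule that gives no reduction and, read literally, doubles her dose early

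*Combined protocol and SAP*

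**What the plan says.** Section 7.1.1 sets the ramp-up at one 850 mg tablet a day for 4 weeks, then two a day subject to a gastrointestinal toxicity evaluation.

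The Grade 1 row of the table in Section 8.2.2 first encourages the woman to stay on treatment for a week. If she will not remain on full dose, she has a week off drug and then repeats the ramp-up ("drug follow the ramp-up procedure If" is the line as extracted; some punctuation is lost, but the sense is clear). The row next covers Grade 1 symptoms that persist or recur in "the ramp-up or at full dose and the patient" "is unwilling to continue, follow" "instructions for Grade 2 toxicity". The referral therefore names women in the ramp-up as well as women at full dose.

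The row for Grade 2 or higher opens with "Reduce to one tablet per day for one week". It continues "If symptoms resolve or are Grade 1 only", "after one week, resume full dose (2 tablets" per day). Its other branch needs symptoms that persist or recur at Grade 2 or "higher, delay study treatment for 4 weeks". The restart, maximum-tolerated-dose and 3-month second-attempt rules come after that hold.

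Section 8.1 forbids splitting tablets and allows limited breaks. Section 8.2 makes the table strict until the woman's own tolerance is known, and guidance after that.

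**The concern.** The Grade 1 row sends two groups to the Grade 2 row, but the Grade 2 row gives workable steps for only one of them. A woman on two tablets gets a real reduction. A woman in the repeat ramp-up does not: she is told to go down to the dose she already takes. The next instruction is two tablets, and the condition for it is one she met on entry.

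What is at stake is the tolerability and timing of one dose step, in a woman who has just said she does not want to continue at the lower dose. It could also cost some adherence. It does not touch the sample size, the power or the month-12 comparison.

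**Working it through.** The plan states no figure on this point to reproduce. The check traces the rules and counts days.

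**Inputs**
- Ramp-up: one tablet a day for 4 weeks, days 1 to 28, so two tablets are due from day 29 (Section 7.1.1).
- First step of the Grade 2 row: one tablet a day for 7 days (Section 8.2.2).
- Next step: two tablets a day if symptoms have resolved or are only Grade 1 (Section 8.2.2).
- No dose exists between one tablet and none (Section 8.1).

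**Dose trace for a woman referred from the repeat ramp-up**
1. Dose on entry: 1 tablet a day.
2. Dose after the reduction step: 1 tablet a day. Reduction = 1 - 1 = 0.
3. After 7 days, if symptoms are Grade 1 or gone: 2 tablets a day. She entered with Grade 1, so she qualifies unless she worsens.
4. The hold and the later maximum-tolerated-dose rule need Grade 2 or higher, so she does not reach them without worsening.

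For a woman referred from full dose, the same row takes her from 2 tablets to 1 and works as written.

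**Timing.** With entry to the Grade 2 row on ramp-up day d, two tablets start on day d + 7.

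Days early = 29 - (d + 7) = 22 - d.

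| Entry day d | Two tablets start | Against day 29 |
|---|---|---|
| 1 | 8 | 21 days early |
| 8 | 15 | 14 days early |
| 15 | 22 | 7 days early |
| 21 | 28 | 1 day early |
| 22 | 29 | same day |
| 23 | 30 | 1 day late |
| 28 | 35 | 6 days late |

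Each early day adds one tablet, so the most is 21 extra tablets.

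**Sensitivity.** Assume the week of encouragement is applied again before referral, with d now the day symptoms recur. Two tablets then start on day d + 14, and days early = 29 - (d + 14) = 15 - d. That is positive only for d = 1 to 14, with at most 14 extra tablets.

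The documents give no distribution of entry days, so neither count can be turned into an expected number.

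**The case against.** The strongest reply is that nobody would follow the literal path. To reduce to one tablet, or to resume full dose, makes sense only for a woman on two, and a clinician would see that the first step does not apply. That is probably the intent. It makes the path unlikely, but it leaves the woman on one tablet with no instruction in the row to which she was expressly sent.

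Other text softens the rule. Twice-daily dosing awaits a toxicity evaluation (Section 7.1.1), though no pass criterion is given there. Section 8.1 allows breaks of up to 4 weeks at a time or 8 weeks in all, to look for the cause of symptoms. Under Section 8.2 the table may already be only guidance for her, because she has tried full dose. Under Section 13.1 she may stop drug for side effects and still be followed. All of this stands and lowers the importance of the point, but none of it says what dose a woman already on one tablet should take next.

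It is also fair that the 21-day maximum requires referral on the first day after a drug-free week.

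A reader might infer that the table exposes women to a new hazard. The documents do not support that: the plan accepts Grade 1 symptoms at full dose, and Section 15.1.7 describes these effects as dose-dependent but transient. A reader might also see a conflict with the restart text later in the Grade 2 row. There is none, because that text applies after a worse course.

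**Conclusion.** The point holds as a minor error in a stated dosing rule. Read literally, Section 8.2.2 gives a woman referred from a repeat ramp-up no reduction, then moves her to two tablets 22 - d days ahead of schedule for entry on days 1 to 21. The maximum is 21 days, or 14 if a further week of encouragement comes first.

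This rests on three assumptions: the site applies the row as worded, her symptoms are Grade 1 or less after the week, and she accepts the higher dose despite her unwillingness. The number of women affected is unknown and the effect on tolerability and safety is small.

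Two wider inferences are not supported. The point does not show that the ramp-up schedules in Section 7.1 are wrong, whether initial or crossover. It also gives no ground for doubting the power or the primary analysis. It is still worth correcting, because the table is to be followed strictly at first and the correction costs almost nothing.

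**What to change.** At the next amendment, add to the Grade 2 row:

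*The one-week reduction and return to full dose applies to women taking two tablets a day. A woman still in a ramp-up stays at one tablet (or takes a break allowed under 8.1) and is not increased to two tablets until 4 weeks at one tablet are complete and symptoms are Grade 1 or less.*

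Leave unchanged the 4-week hold, the maximum-tolerated-dose and 3-month second-attempt rules, and Section 8.2.1 on grade 3 or 4 diarrhea. Do not extend the 3-month wait to women with Grade 1 symptoms. The table reaches it only after persistent Grade 2 or higher symptoms, a hold and a failed repeat ramp-up. Using it earlier could leave some women on half dose for 3 of the 12 months before the primary endpoint.

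Cost: a short table edit, with no new visits, data or analysis. The downside is that a few women may reach full dose up to 3 weeks later than under the literal rule. With Grade 1 or lower symptoms, that is still no later than the ramp-up schedule, apart from any break taken.
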